## 5.4.1 Primary Endpoint Analyses

The primary safety analysis (Time to MACE using the Total Time Analysis Set) will be the only analysis performed at the interim analysis as outlined in Section 6. All other analyses will be performed at Study Completion, see Section 8 for definition of Study Completion.

## **Primary Safety Analyses**

• Time to MACE(Non-inferiority): The estimate of the hazard ratio of lorcaserin HCl to placebo and the corresponding one-sided 97.5% confidence interval (CI) will be calculated. Non-inferiority of lorcaserin HCl to placebo will be declared if the upper limit of the 97.5% CI is less than the non-inferiority margin of 1.4. The Total Time Analysis Population will be used as the primary analysis at the time of the Interim Analysis. (revised per Amendment 02) The On-Treatment Analysis Set and the On-Treatment plus 30 Days Analysis Set will be used as a sensitivity analysis at Study Completion. (revised per Amendment 02)

## **Primary Efficacy Analyses**

• Time to MACE+ (Superiority): The estimate of the hazard ratio of lorcaserin HCl to placebo and the corresponding two-sided 95% CI will be calculated. The Total Time Analysis Population will be used as the primary analysis. (revised per Amendment 02) The On-Treatment Analysis Set and On-Treatment plus 30 Days Analysis Set will be used as a sensitivity analysis at Study Completion. (revised per Amendment 02)

## 5.4.1.1 Additional Sensitivity Analyses at Study Completion

- **Time to MACE (Non-inferiority):** The primary safety analysis above, which will be conducted at the interim analysis, will be repeated at study completion as a sensitivity analysis.
- Time to MACE (Superiority): The estimate of the hazard ratio of lorcaserin HCl to placebo and the corresponding one-sided 97.5% confidence interval (CI) will be calculated. Superiority lorcaserin HCl to placebo will be declared if the upper limit of the 97.5% CI is less than 1. The Total Time Analysis Set, the On-Treatment Analysis Set, and the On-Treatment plus 30 Days Analysis Sets will be used.
- The incidence rate difference and the incidence rate ratio between lorcaserin and placebo will also be analyzed as supportive analysis for each of the primary endpoints above. The adjusted risk difference (incidence rate difference) and relative risk (incidence rate ratio) along with their respective 95% CI will be estimated using a Poisson regression model (using PROC GENMOD in SAS) with a robust error variance (sandwich error estimator). The model will include factors for treatment and stratification variable (presence of established CV disease or CV risk factors without established CV disease). The Total Time Analysis Set, the On-Treatment Analysis Set, and the On-Treatment plus 30 Days Analysis Sets will be used.
- Subjects that start another weight reduction medication or had bariatric procedure: For MACE and MACE+ endpoints using the Total Time Analysis Set. In this sensitivity analysis subjects will be censored when the subject starts another weight reduction medication or undergoes a bariatric procedure.
- Subjects who permanently down titrate from BID dosing to QD dosing: For MACE and MACE+ endpoints using the On-treatment and On-treatment plus 30 days Analyses Sets. In this sensitivity analysis events will be not counted when the subject is on QD dosing.
- **Subjects who prematurely discontinued:** For the MACE (Superiority) and MACE+ endpoints, multiple imputation will be used to impute censored data for those subjects who are lost to follow-up. The Total Time Analysis Set will be used.

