9.7.1.6 Primary Safety and Key Secondary Efficacy Analyses (revised per Amendment 02)

The primary endpoints, MACE, and MACE+, will be analyzed using a Cox proportional hazards model that includes factors for treatment and stratification variable (presence of established CV disease or CV risk factors without established CV disease). (revised per Amendment 02) For secondary and exploratory endpoints a 2-sided $\alpha = 0.05$ significance level will be used. The MACE analysis (“interim” analysis) will be conducted when 460 adjudicated MACE events have been recorded; the other analyses will be conducted when 1401 adjudicated MACE+ events have been recorded, and the study has completed. (revised per Amendment 02)

Sequential Gatekeeping Testing Procedure (revised per Amendment 02)

The following closed sequential gatekeeping testing procedure (SGTP) will be used to control the family-wise error rate (FWER) at $\alpha = 0.05$ (2-sided) in testing the 2 primary endpoints (MACE and MACE+) and 1 key secondary endpoint, conversion to T2DM. (revised per Amendment 02)

Let H_{01} be the gatekeeping null hypothesis for noninferiority testing of the MACE endpoint using a noninferiority margin of 1.4.

Let H_{02} , and H_{03} be the null hypotheses for superiority testing: MACE+ and conversion to T2DM, respectively. (revised per Amendment 02)

The SGTP testing hierarchy is presented below. (revised per Amendment 02)

- STEP1: At the interim analysis, test the noninferiority hypothesis for MACE, H_{01} ($\alpha = 0.025$, 1-sided). If H_{01} is rejected, then proceed to STEP2, otherwise stop testing and the trial will be stopped.
- STEP2: At study completion, the hypotheses H_{02} ($\alpha = 0.05$, 2-sided), is tested first. If the hypothesis is rejected, then proceed to test H_{03} ($\alpha = 0.05$, 2-sided). If H_{02} is not rejected, then testing stops at this point.

[Figure 3](#) presents the SGTP. (revised per Amendment 02)

Flowchart for the Sequential Gatekeeping Testing Procedure

[figure not shown]

Figure 3 Flowchart for SGTP

MACE = major adverse cardiovascular events, MACE+ = MACE or hospitalization for unstable angina or heart failure, or any coronary revascularization; SGTP = sequential gatekeeping testing procedure; T2DM = type 2 diabetes mellitus.

PRIMARY ENDPOINT ANALYSES

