## **5.1.1 Primary Endpoints**

- Time from randomization to first occurrence of MACE (first occurrence of any of the following events: MI, stroke, or CV death) at Interim Analysis only.
- Time from randomization to first occurrence of MACE+ (first occurrence of any of the following events: MACE or hospitalization for unstable angina or HF, or any coronary revascularization)

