## **5.3.3** Multiple Comparisons/Multiplicity

This study has two primary endpoints; MACE and MACE+. The following closed sequential gatekeeping testing procedure (SGTP) will be used to control the family-wise error rate (FWER) at  $\alpha = 0.05$  (two-sided) in testing the two primary endpoints (MACE and MACE+) and one key secondary endpoint, conversion to T2DM (revised per Amendment 02).

Let  $H_{01}$  be the gatekeeping null hypothesis for non-inferiority testing of the MACE endpoint using a non-inferiority margin of 1.4 for the hazard ratio.

Let  $H_{02}$ , and  $H_{03}$  be the null hypotheses for superiority testing: MACE+ and conversion to T2DM, respectively.

The SGTP testing hierarchy is presented below.

STEP1: At the interim analysis, test the non-inferiority hypothesis for MACE,  $H_{01}$  ( $\alpha = 0.025$ , one-sided). If  $H_{01}$  is rejected, then proceed to STEP2, otherwise stop testing and the trial will be stopped. This step will be performed as an interim analysis, see Section 6 for further details

• STEP2: At study completion, the hypothesis  $H_{02}$  ( $\alpha = 0.05$ , two-sided) is tested first. If the hypothesis is rejected then proceed to test  $H_{03}$  ( $\alpha = 0.05$ , 2-sided). If  $H_{02}$  is not rejected then testing stops at this point..

Figure 2 presents the SGTP (revised per Amendment 02)

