#### Test MACE non-inferiority (a=0.025 1-sided) Step 1 Performed at STOR Interim Analysis Yes Step 2 Performed at MACE+ Study Completion superiority (a=0.05 2-sided) Significant? STOR Testing Conversion T2DM superiority (a=0.05 2-sided)

#### Flowchart for the Sequential Gatekeeping Testing Procedure

Figure 2 Flowchart for SGTP

MACE = major adverse cardiovascular events, MACE+ = MACE or hospitalization for unstable angina or heart failure, or any coronary revascularization; Step 1 will be performed when 460 adjudicated MACE events occurred, at the Interim Analysis. Step 2 will be performed upon Sponsor Notification of Study Completion which will occur once 1401 MACE+ events, and 2.5 years median treatment duration.

Analysis of other secondary endpoints will be used to support the results of primary analyses, thus no multiplicity adjustment will be performed.

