#### 8.5.2 Censoring at Study Completion

8.5.2.1 Censoring for MACE, MACE+, each Component of MACE, and All-Cause Mortality

If non-inferiority between lorcaserin HCl and placebo is confirmed at the interim analysis, then the study will be continued to observe; 1401MACE+ events at approximately 54 months from the start of the study and 2.5 years median treatment duration.

algorithms

MACE non-inferiority and superiority, each component of MACE, and All-cause mortality will analyzed at study completion as part of additional sensitivity analyses. The censoring algorithm is the same for these endpoints but differs by Analysis Set as described in the Table 6, and see Appendix 13.2 for diagrams of censoring algorithms.

For subjects who experienced an event, their time-to-event will be determined from the randomization date (for the Total Time Analysis) and the start date of study drug (for the On-Treatment and On-Treatment + 30-Days Analyses), to the date of the event. The censoring variable will be, CENSORED=0. For subjects who do not experienced an event, the censoring time will be determined from the randomization date (for the Total Time Analysis) and the start date of study drug (for the On-Treatment and On-Treatment + 30-Days Analyses), to the date described in Table 6, along with a matching censoring variable, CENSORED=1.

Table 6 Censoring Date For subjects who did not experienced an event at Study Completion

Table o Ce	ensoring Date For subjects who did not ex	xperienced an event at Study Completion
Analysis		
Set a	Completed the Study	Withdrawal From Study Follow-up
Total Time	In the Final Study Disposition Form use	In the Final Study Disposition Form use the
on Study	the date from , Date of Final Sponsor	date from , Date of Final Sponsor
	Notification/Premature Study	Notification/Premature Study Discontinuation
	Discontinuation	and
	and status is equal to completed	status for discontinuation equals any of the
		following;
		Withdrew Consent
		Lost to Follow up
		Study Terminated by Sponsor
		• death (except for All Cause-mortality)
		• Other
On-	Date of last dose from Study	Date of last dose from Study Medication Form
Treatment +	Medication Form + 30 Days	+ 30 Days
30 Days		
-		
On-	Date of last dose from Study Medication	Date of last dose from Study Medication Form
Treatment	Form	
a See Section	5.2.1 for definitions of Analysis Sets and A	Appendix 13.5.2 for diagrams of censoring

algorithms

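### SAP 5.4.1.1 sets a rule for declaring MACE superiority at study completion in three analysis sets, outside the gatekeeping sequence and without family-wise control

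*SAP*

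**What the plan says.** SAP 5.3.3 and Protocol 9.7.1.6 define one sequential procedure. H01 is MACE non-inferiority at the interim (margin 1.4, one-sided 0.025), H02 is MACE+ superiority at completion, and H03 is superiority on conversion to T2DM. The SAP says that family-wise error is controlled at 0.05 two-sided "in testing the two primary endpoints (MACE and MACE+) and one key secondary endpoint, conversion to T2DM". If H02 "is not rejected then testing stops at this point". MACE superiority is not one of the hypotheses.

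SAP 5.1.1 restricts the role of MACE as a primary endpoint; its entry ends "MI, stroke, or CV death) at Interim Analysis only".

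SAP 5.4.1.1 then lists a MACE superiority analysis at study completion, based on a one-sided 97.5% CI, with this rule: "Superiority lorcaserin HCl to placebo will be declared if the upper limit of the 97.5% CI is less than 1". On the populations it says: "The Total Time Analysis Set, the On-Treatment Analysis Set, and the On-Treatment plus 30 Days Analysis Sets will be used". It does not refer to MACE+, to the sequence or to multiplicity.

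SAP 8.5.2.1 repeats the label: "MACE non-inferiority and superiority, each component of MACE, and All-cause mortality will analyzed at study completion as part of additional sensitivity analyses".

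The multiplicity waiver that follows the flowchart in SAP 5.3.3 reads: "Analysis of other secondary endpoints will be used to support the results of primary analyses, thus no multiplicity adjustment will be performed". SAP 5.4.3 gives a similar waiver for secondary endpoints. MACE superiority is not among the secondary endpoints in SAP 5.1.3.

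**The concern.** The label and the rule point in opposite directions. A sensitivity analysis examines whether a primary result is robust. Repeating MACE non-inferiority at completion, the first item in SAP 5.4.1.1, fits that description. MACE superiority does not: the plan has no primary MACE superiority analysis for it to support, so it is a new hypothesis.

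The wording is also that of a confirmatory test. It has the same form as the non-inferiority rule in SAP 5.4.1. By contrast, MACE+, T2DM conversion and the secondary time-to-event endpoints are described only through estimates and intervals. The multiple-imputation item in SAP 5.4.1.1 then pairs MACE superiority with MACE+, as if it were a main result needing its own robustness check.

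At stake is what may be said if MACE+ misses. MACE is the narrower and harder composite. The approved SAP would contain a prespecified rule supporting a declared MACE benefit, possibly in an on-treatment set only, while SAP 5.3.3 says that testing has ended.

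**Working it through.** **Inputs from the documents**
- MACE events at completion: about 600 (Protocol 9.7.3)
- MACE+ events: 1401 (SAP 4)
- Allocation: 1:1 (SAP 3.3)
- MACE superiority: one-sided 0.025 in each set (SAP 5.4.1.1)
- MACE+: two-sided 0.05, so 0.025 in the direction of benefit (SAP 5.3.3)

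**Assumptions not in the documents**
- The share w of MACE events that are also the subject's first MACE+ event: 1.0 to 0.8
- The correlation between the MACE statistics in the three sets: 0.95 to 0.8

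**1. The plan's own figure.** Each step of the sequence is at full alpha and is reached only if the previous step rejects. A false superiority finding therefore has probability at most 0.025 in the direction of benefit. A null simulation of one million runs, with the interim gate at 460 events, gave 0.025. The stated control is reproduced for H01–H03.

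**2. Correlation of the MACE and MACE+ statistics.** With score variance proportional to events,

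ρ = w × 600 / √(600 × 1401) = w × √(600/1401)

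- w = 1.0: ρ = 0.654
- w = 0.8: ρ = 0.524

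The first value is an upper limit. A MACE that follows an earlier revascularization or qualifying hospitalization is not the first MACE+ event.

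**3. MACE superiority added, Total Time set only.** With both nulls true,

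P(either) = 0.025 + 0.025 − P(both below −1.96)

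| ρ | P(both) | P(either) | P(MACE only) |
|---|---|---|---|
| 0.654 | 0.0073 | 0.0427 | 0.0177 |
| 0.524 | 0.0050 | 0.0450 | 0.0200 |

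The last column is 0.025 − P(both): MACE declared although MACE+ failed. Adding the interim gate in simulation gave 0.043 to 0.046 for P(either), so the gate hardly matters in this direction.

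**4. Any of the three sets suffices (worst case).** This uses a normal simulation with equal correlation b between the sets. Each on-treatment statistic is given correlation ρ × b with MACE+.

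| ρ | b | P(MACE+ or any MACE set) |
|---|---|---|
| 0.654 | 0.95 | 0.053 |
| 0.654 | 0.80 | 0.065 |
| 0.524 | 0.95 | 0.056 |
| 0.524 | 0.80 | 0.067 |

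If the on-treatment sets are tied slightly less to MACE+ (0.35 to 0.38 instead of 0.42), the last row becomes 0.068. A separate simulation built on event shares gave 0.055 to 0.067. It assumed 50–80% of MACE events on treatment and 60–85% within treatment plus 30 days.

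The chance of a false MACE declaration in at least one set is about 0.037 to 0.049, so under this reading the nominal 0.025 for that single hypothesis is exceeded too.

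**5. Where the boundary lies.** At 600 events, exp(−1.96 × 2/√600) = 0.852. An observed hazard ratio just below 0.852 would trigger the declaration.

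**The case against.** The strongest reply is that the plan already puts this analysis outside the confirmatory set. The heading of SAP 5.4.1.1 and the text of SAP 8.5.2.1 both call it a sensitivity analysis. No objective in the protocol asks for MACE superiority, and SAP 5.1.1 ends the primary role of MACE at the interim. On this view one verb was carried over from the non-inferiority rule and no claim is intended. The sponsor may well mean that. But the label cannot settle the matter while the sentence beneath it says that superiority will be declared, and neither multiplicity waiver covers this analysis.

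Three stronger readings are tempting, and the documents do not support them:
- **That the stated family-wise control fails.** It does not. SAP 5.3.3 defines the family as three hypotheses, and control holds for them. The inflation appears only when MACE superiority is counted as well.
- **That the MACE test has no error control at all.** Each set is tested at a nominal one-sided 2.5%, and a failed interim non-inferiority test stops the trial.
- **That the SAP expressly allows a MACE claim after MACE+ fails.** SAP 5.4.1.1 states no exemption, and the stop in SAP 5.3.3 could be read as barring the claim. The two sections conflict; neither overrides the other.

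The objection to the three-set figure also stands in part. The plan says only that the sets will be used, not that any one suffices, and for MACE non-inferiority, MACE+ and the MACE+ components Total Time is primary. The Total Time figure is the better supported of the two.

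**Conclusion.** The point holds as a conflict within the SAP. A formal rule for declaring MACE superiority sits under a sensitivity heading, is not tied to the gatekeeping sequence, and has no family-wise control.

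Against 2.5% for the sequence alone, the null one-sided chance of a superiority declaration on MACE+ or MACE is about 4.3–4.5% with Total Time only. This rests on ρ of 0.65–0.52, the higher value requiring every MACE to be the first MACE+ event. The figure of about 5.3–6.8% is a worst case: it needs between-set correlations of 0.95–0.8, which the documents do not give, and a reading in which any one set suffices. The direction does not depend on these assumptions; the exact size does.

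Sample size, event targets and stated powers are unaffected.

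**What to change.** In SAP 5.4.1.1, replace the sentence that declares MACE superiority with:

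> The hazard ratio and nominal 95% CI will be reported; this analysis is outside the gatekeeping procedure and no superiority claim will be made.

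In the same item, name the Total Time Analysis Set as the main set and the two on-treatment sets as supportive. The multiple-imputation item can stay, read in the same descriptive sense, and SAP 8.5.2.1 already agrees.

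Placing MACE superiority inside the sequence would also restore control. That is a design choice, would need edits to SAP 5.3.3 as well, and is not needed to resolve the conflict.

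The cost is that an unprotected claim is given up. No analysis is lost and no event count changes.

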## 5.2 STUDY SUBJECTS

#### **5.2.1** Definitions of Analysis Sets

The number (percent) of subjects included in each analysis set will be presented by analysis set, treatment group and overall. The description of the analysis data sets are:

- The Safety Analysis Set: will be the group of subjects who received at least one dose of study drug and had at least one post dose safety assessment.
- The Intent-to-Treat (ITT) Set: will be the group of all randomized subjects regardless of whether they took study drug or not. This is the same as the Full Analysis Set.
- Total Time Analysis Set: Using the ITT, events are counted that occur while subjects are on and off treatment. Subjects with no events will be censored at their last study contact or at the visit following Sponsor Notification of Study Completion, whichever

- occurs first. This analysis set will be used for the primary analysis. See Section 8.5 for censoring algorithm.
- On-Treatment plus 30 Days Analysis Set: Using the ITT, events are counted that occur
  while subjects are "on treatment" and up to 30 days from their last dose. Subjects with
  no events who discontinue early or complete the study will be censored at their last dose
  date plus 30 days. See Section 8 for definition of "on treatment" and Section 8.5 for
  censoring algorithm.
- On-Treatment Analysis Set: Using the ITT, events are counted that occur while subjects are "on treatment". Subjects with no events who discontinue early or complete the study will be censored at their last dose date. See Section 8 for definition of "on treatment" and Section 8.5 for censoring algorithm.
- Prediabetes Analysis Set: This set includes all subjects in the ITT set without a history of any type of diabetes and who are prediabetic at Baseline (defined in Section 8).
- Nondiabetes Analysis Set: This set includes all subjects in the ITT set without a history of any type of diabetes at Baseline (defined in Section 8).
- T2DM Analysis Set: This set will be all subjects in the ITT who have T2DM at Baseline (defined in Section 8).
- FDA-defined Valvulopathy Analysis Set: This set will be all subjects in the ITT without FDA- defined valvulopathy at Baseline (defined in Section 8.4). The data from the ECHO sub-study will be pooled with the ECHO data from the 3 pivotal lorcaserin HCl studies (APD356-009, APD356-010, and APD356-011).

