#### Secondary Prevention Risk Scores

The Risk score is calculated by totaling the number of risk factors a subject has at baseline and categorizing the total score into  $0, 1-2, \text{ or } \ge 3$ . See table below.

Risk Factor	Points
Congestive heart failure	1
Hypertension	1
Age ≥ 75 years	1
Diabetes mellitus	1
Prior stroke	1
Prior CABG	1
Peripheral arterial disease	1
Renal dysfunction (eGFR <60 mL/min 1.73 m 	1
Current smoker	1
Prior MI	1

- On treatment: This definition applies to the "On-Treatment" and "On-Treatment plus 30 Days" Analyses Sets described in Section 5.2.1. A subject is considered to be "on treatment" while the subject is on study drug. If a subject permanently discontinues study drug, the subject is considered to be "off treatment". If a subject is taking BID dosing or QD dosing, or stops and restart study drug then the subject is still considered to be "on treatment"
- Subject who Completed the Study on Study Drug: A subject is considered to have completed the study on study drug, if the last dose date for the subject falls 1 day prior or on/after the date of Sponsor notification of Study Completion and "Subject Status at Final Sponsor Notification Visit/Premature Study Discontinuation or "Subject Status at Final 30-Day Follow-up Visit" = "Completed", "Death".
- Subject who Completed the Study: A subject is considered to have completed the study, if in the Final Study Disposition CRF, "Subject Status at Final Sponsor Notification Visit/Premature Study Discontinuation Visit" = "Completed", "Death", or "Subject Status at Final 30 Day Follow-up Visit" = "Completed" or "Death". For these subjects the EOT is the same as the EOS visit.

- Study Completion: Sponsor Notification of Study Completion will occurred once 1401 MACE+ adjudicated events, and 2.5 years median treatment duration.
- Subjects without Any Type of Diabetes at Baseline: Subject must meet the following conditions;
  - o On the Diabetes History Form "Clinical diagnosis of diabetes?" = "No" and
  - o Not initiated any diabetes treatment prior to or at Baseline and
  - o None of the following where available
    - o HbA1c  $\geq$  6.5% in all central or local labs assessments prior to or at Baseline and
    - $\circ$  FPG  $\geq$  126 mg/dL (7.0 mmol/L) in all central or local labs assessments prior to or at Baseline and
    - o 2-hour plasma glucose ≥ 200 mg/dL(11.1mmol/L) by an OGTT test prior to or at Baseline and

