#### 8.5.2.4 Censoring for Sensitivity Analysis Time-to-Event Endpoints

Subjects that start another weight reduction medication or has a bariatric procedure: MACE and MACE+ endpoints will be analyzed using the Total Time Analysis Set.

For subjects who experienced an event and did not start on another weight reduction medication or did not have bariatric surgery, their time-to-event will be determined from the randomization date to the date of the event. The censoring variable will be, CENSORED=0.

For subjects who experienced an event and started on another weight reduction medication or undergoes bariatric surgery, the censoring variable will be, CENSORED=0, if date of event is either prior to date of starting a weight reduction medication or having bariatric surgery or the event occurred after having stopped taking a weight reduction medication. Their time-to-event time will be determined from randomization date to date of the event. The censoring variable will be, CENSORED=1, if the date of event is equal to or greater than date of having bariatric surgery or the event date occurred while on a weight reduction medication. The censoring time will be determined from the randomization date to the earliest date of starting another weight reduction medication and/or having bariatric surgery. If date of starting another weight reduction medication or having bariatric surgery is prior to the randomization date, then censoring time will be set to the randomization date.

For subjects who do not experience an event and did not start on another weight reduction medication or did not have bariatric surgery, the censoring time will be determined from the randomization date to the date described in the Table 6 using the Total Time on Study Analysis Set, along with a matching censoring variable, CENSORED=1.

For subjects who do not experience an event and start on another weight reduction medication or undergoes bariatric surgery, the censoring time will be determined from the randomization date to the date of starting a weight reduction medication or the date of the bariatric surgery, along with a matching censoring variable, CENSORED=1. If date of starting another weight reduction medication or having bariatric surgery is prior to the randomization date, then censoring time will be set to the randomization date.

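### The QD-dosing sensitivity analysis drops events on QD without removing the QD follow-up, so its hazard ratios shift if QD time differs between arms

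*SAP*

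**What the plan says.** - **The QD analysis.** SAP Section 5.4.1.1 covers subjects who permanently down-titrate: "For MACE and MACE+ endpoints using the On-treatment and On-treatment plus 30 days Analyses Sets". The only handling rule is "In this sensitivity analysis events will be not counted when the subject is on QD dosing".
- **Status of QD time.** The definition of on-treatment status in SAP Section 8 includes QD dosing: "If a subject is taking BID dosing or QD dosing, or stops and restart study drug then the subject is still considered to be" in that status.
- **End of follow-up.** For the On-Treatment set, SAP Section 5.2.1 says "Subjects with no events who discontinue early or complete the study will be censored at their last dose date". Table 6 (Section 8.5.2.1) gives the same date, "Date of last dose from Study Medication Form", and adds 30 days for the On-Treatment plus 30 Days set. Neither place mentions the switch to QD.
- **The neighbouring analysis.** For weight-reduction drugs and bariatric procedures, Section 5.4.1.1 says "In this sensitivity analysis subjects will be censored when the subject starts another weight reduction medication or undergoes a bariatric procedure". Section 8.5.2.4, which holds the censoring rules for sensitivity analyses, covers that analysis and has no entry for QD.
- **How subjects reach QD.** Protocol Section 9.4.5.1 allows reduced dosing for intolerable nonserious AEs that the investigator attributes to study drug. Prolonged QD follows three failed attempts to return to BID. Subjects on prolonged QD may later go back to BID.

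**The concern.** Dropping an event while leaving the subject in the risk set turns the event into event-free time. It affects everyone on QD, not only those whose events are dropped, because all QD person-time sits in the denominator with nothing able to enter the numerator. Both arms' rates fall. If one arm spends more time on QD, its rate falls further and the hazard ratio moves in its favour for a reason unrelated to the drug's effect. The analysis is meant to show whether the MACE and MACE+ results hold up at full dosing, and in that case it could not show this reliably.

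**Working it through.** **The plan's own figures.** The documents give no number for the QD analysis. The design figures for the two endpoints reproduce with the Schoenfeld formula and are not in dispute:

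- MACE: 4 × (1.960 + 1.645)² / (ln 1.4)² = 459.1, rounded up to 460 events, as stated.
- MACE+: z = (√1401 / 2) × |ln 0.85| − 1.960 = 1.08, which is 86.0% power against the stated figure of more than 85%.

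**Formula.** Take an arm with constant hazard λ, on-treatment person-time T, and a share f of T spent on permanent QD.

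- As written: counted events λT(1 − f), time kept about T, so the rate is λ(1 − f).
- Censored at the switch: counted events λT(1 − f), time T(1 − f), so the rate is λ.
- Apparent hazard ratio as written ≈ true HR × (1 − fL) / (1 − fP), where L is lorcaserin and P is placebo.

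**Illustration.** Use the MACE design rate of 1.5% per year, a true HR of 1.00, and 10,000 person-years per arm (an illustrative figure), so 150 events are expected in each arm. Assume QD shares of 10% and 2%. Counted events are 135 and 147.

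- Over 10,000 person-years each: 1.35% vs 1.47%, ratio 0.918.
- Over 9,000 and 9,800 person-years: 1.50% vs 1.50%, ratio 1.00.

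**Range by formula.** The shares are assumptions about person-time.

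| QD share, lorcaserin vs placebo | Factor | True HR 1.00 becomes | True HR 0.85 becomes |
|---|---|---|---|
| 5% vs 5% | 1.000 | 1.00 | 0.85 |
| 5% vs 2% | 0.95/0.98 = 0.969 | 0.97 | 0.82 |
| 10% vs 5% | 0.90/0.95 = 0.947 | 0.95 | 0.81 |
| 10% vs 2% | 0.90/0.98 = 0.918 | 0.92 | 0.78 |

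**Check by simulated Cox models.** Here the percentages are shares of subjects who switch, all within the first year (assumed). The first three rows use 12,000 subjects, 3.5% per year, 15-month accrual, 54 months, 5% annual drop-out and 40 replicates, with Monte Carlo error of about 0.01. The last two rows use 1.5% per year and 12 runs of 120,000 subjects.

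| Subjects on QD | True HR | As written | Censored at switch | Ratio |
|---|---|---|---|---|
| 10% vs 10% | 1.00 | 0.989 | 0.989 | 1.00 |
| 5% vs 2% | 1.00 | 0.965 | 0.991 | 0.97 |
| 10% vs 2% | 1.00 | 0.932 | 1.004 | 0.93 |
| 10% vs 2% | 1.00 | 0.936 | 1.007 | 0.93 |
| 10% vs 2% | 1.20 | 1.109 | 1.194 | 0.93 |

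In the third row the simulated person-time shares were 8.4% and 1.7%. The formula then predicts 0.916/0.983 = 0.932, which matches.

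**The case against.** The best defence is that not counting an event is this sponsor's shorthand for censoring. Protocol Section 9.7.1.6 describes the weight-reduction analysis as not counting later events, and the SAP carries that out by censoring. The censoring diagrams in Appendix 13.2 are not visible in the copy reviewed, and SAP Section 9 places programming rules in separate documents, so a QD date may exist elsewhere. This stands as a reason to check. It does not rescue the SAP text: the weight-reduction analysis was given an explicit statement and an algorithm, QD was given neither, and the general rules that then apply keep the time.

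Other points stand:

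- The hazard ratio moves only if QD time differs by arm, and no document gives a QD rate.
- Prolonged QD is a narrow group. Reduced dosing came with Amendment 01 in August 2015, about 20 months after the planned December 2013 start, so first-year switching cannot hold for the earliest enrollees. The true shares may be small.
- Because subjects may return to BID, one censoring date would discard later BID time and events that the present wording counts.
- Recovery of the true value in the simulations assumes that switching is unrelated to risk.

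**Conclusion.** The point holds as a minor defect. Read with the on-treatment definition and Table 6, the stated rule deletes QD events and keeps QD time, so the hazard ratio is multiplied by about (1 − fL)/(1 − fP). Under assumed shares this means no change when they are equal, about 0.97 at 5% vs 2%, and about 0.92 to 0.94 at 10% vs 2%. These sizes rest on a roughly constant hazard and on QD shares that the documents do not supply.

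A reader might infer three stronger things, and the documents support none of them:

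- **That the SAP expressly retains QD follow-up.** It does not say so; retention follows from the other rules and the absence of a QD rule.
- **That the hazard ratios are necessarily pulled toward benefit.** Protocol Section 9.4.5.1 makes more QD time on lorcaserin plausible, since QD follows AEs attributed to study drug. It does not establish it.
- **That the trial's safety or efficacy conclusion is at risk.** MACE noninferiority is decided at the interim on the Total Time set (SAP Sections 5.4.1 and 6.1.1), and MACE+ superiority also uses Total Time. The QD analysis lies outside the gatekeeping procedure in SAP Section 5.3.3. The unmodified On-Treatment analyses, which count QD events, are also planned.

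**What to change.** Replace the sentence in SAP Section 5.4.1.1 with one of two rules, and add it to Section 8.5.2.4:

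1. Censor follow-up at the start of permanent QD dosing.
2. Remove QD intervals from the risk set, with re-entry for subjects who resume BID.

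The second stays closer to the present wording, which excludes events only while the subject is on QD. Either way, define the date on which permanent QD begins and say how the 30-day window applies in the On-Treatment plus 30 Days set.

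The cost is about a sentence and its programming. Protocol Section 9.4.5.1 has use of dose reduction captured in the eCRF, and SAP Section 5.6.1 plans average dose by month, which suggests that dated dosing data exist; confirm that the switch date can be derived. The statistical drawback is that censoring may be informative, because AEs trigger down-titration. Report the result beside the unmodified On-Treatment analyses, with QD person-time by arm. No dosing rule changes.
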